4. ANALYSIS SETS

One (1) analysis dataset will be used for study all analyses: Full Analysis Set (FAS).

Additional analysis sets or subgroups of interest may be required as part of post-hoc analyses. These will be detailed in the CSR.

The number and percentage of subjects in each analysis set will be summarised.

4.1 **Analysis Set Descriptions**

4.1.1 **Full Analysis Set (FAS)**

The FAS will comprise all subjects enrolled into the study.

5. PROTOCOL DEVIATIONS

Analysis Set: Full Analysis Set (FAS)

All deviations recorded during the trial will be categorised as Minor and Major. The major deviations will be further assessed in order to identify critical deviations. A critical protocol deviation will be defined as a deviation that contributes to the following:

- Treatment compliance below 80 % during the treatment period.
- No sputum samples at 2 visits.

6. SUBJECT DISPOSITION

Analysis Set: Full Analysis Set (FAS)

A listing of subject disposition will present:

- Date of informed consent
- Date of treatment commencement
- Date of treatment discontinuation
- Study day of treatment discontinuation (Days after first dose)
- Last visit before treatment discontinuation
- Primary reason for discontinuation of treatment
- Date of study completion/End of participation
- Study day of study completion/End of participation (Days after first dose)
- Last visit before study completion/End of participation
- Primary reason for ending study participation

Subject withdrawal information, including date and reason for treatment termination, will also be listed in a separate listing.

The number and percentage of subjects entering and discontinuing the study will be summarised along with the reason for discontinuation. The subject disposition summary table will include:

- Number of subjects enrolled
- Number of subjects who received at least one dose of study medication
- Number of subjects who completed 24 weeks treatment
- Number of subjects who completed 48 weeks treatment
- Number of subjects who completed the full study
- Number of subjects withdrawn early
- Reason for early withdrawal

7. DEMOGRAPHIC AND BASELINE INFORMATION

Analysis Set: Full Analysis Set (FAS)

7.1 Demographics

7.1.1 *Definition of variables*

- Age (years)
- Sex
- Race (White/Asian/Black/American Indian or Alaska Native/Native Hawaiian or Other Pacific Islander)
- Female reproductive status
- Male reproductive status
- Smoking status (Previous/Current/Never)

7.1.2 *Biostatistical methods*

Demographic data will be listed and summarised.

7.2 Baseline Characteristics

Select baseline characteristics will be presented in a summary table, including:

- Height
- Weight
- BMI
- FVC
- FEV1

7.3 Medical history

All medical history data will be listed. Medical history (other than disease under study) will be coded using the Medical Dictionary for Regulatory Activities, MedDRA[®] and summarised by system organ class (SOC) and preferred term (PT).

7.4 Pregnancy Test

Pregnancy test data will be listed for all women of childbearing potential.

7.5 Eligibility

All eligibility data will be listed.

7.6 Disease specific Medical History

7.6.1 *Definition of variables*

From the CRFs:

- Date of microbiological diagnosis of current pulmonary infection
- Type of NTM (Mycobacterium avium complex (MAC) | Mycobacterium abscessus)
- Body weight at time of initial diagnosis
- Age at time of initial diagnosis
- Forced Vital Capacity (FVC) at time of initial diagnosis
- Forced Expiratory Volume in 1 second (FEV1) at time of initial diagnosis
- ATS/IDSA 2017 criteria fulfilled

Derived:

- Duration of infection: defined as the number of days from the date of initial diagnosis to the date of informed consent.

7.6.2 *Biostatistical methods*

NTM history data will be listed for all subjects.

An NTM History summary table will present:

- Duration of infection
- Frequency of NTM type
- Forced Vital Capacity (FVC) at time of initial diagnosis
 - FVC (L)
 - Relative FVC (%)
- Forced Expiratory Volume in 1 Second (FEV1) at time of initial diagnosis:
 - FEV1 (L)
 - Relative FEV1 (%)
- Number of subjects with each ATS/IDSA2017 criterion

7.7 NTM Sampling

All NTM sampling history will be listed.

8. TREATMENT EXPOSURE

Analysis Set: Full Analysis Set (FAS)

8.1.1 *Definition of variables*

From the CRFs:

- Confirmation of subject training
- Date/time of clinic study drug administration
- Dispense data
 - Number of kits dispensed by visit
- Compliance data
 - Number of used vials
 - Number of unused vials
 - Number of used lost vials
 - Number of unused lost vials
 - Compliance (visit level)
- Dose change details
 - Start date of changed dose regimen
 - Number of doses
 - Frequency of dose
 - Reason for changed dose

Derived:

- Number of subjects who had a break in treatment after completing Week 24 and commencing the remaining treatment period to Week 48
- Duration of exposure:
 $date\ of\ treatment\ discontinuation - date\ of\ first\ treatment + 1$
- Overall compliance (%)

$$\frac{Number\ of\ used\ vials}{Treatment\ days * } \times 100$$

* $treatment\ days = (date\ of\ end\ of\ treatment - date\ of\ visit\ 2) + 1$

8.1.2 *Biostatistical methods*

All treatment exposure data, including kit dispense, compliance, study drug administration and dose change details, will be listed.

Duration of exposure and compliance (by visit and overall) will be summarised.

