Participating subjects will be encouraged to contact the clinic between visits if they experience adverse events (AEs), worsening of their condition or have any other concerns. If needed, unscheduled visits will be conducted at investigator's discretion.

A schedule of study assessments is available in [Table 1](#).

Treatment with inhaled molgramostim will be given at a dosage of 300 µg once daily for 48 weeks. All subjects in the trial initially consented to 24 weeks of treatment. All enrolled subjects continuing with 48 weeks of treatment will re-consent and follow the visits schedule as described above.

Subjects that do not wish to continue to 48 weeks of treatment will end treatment after 24 weeks (visit 8) and will attend the follow-up visit 12-weeks later as per the visit schedule outlined in Protocol Version 2.0 or 3.0.

Subjects who complete the initial 24-week treatment period prior to the approval of Protocol Version 4.0 will proceed to the 12 week follow up as per the visit schedule in Protocol Version 2.0 or 3.0. Once Protocol Version 4.0 is approved they will be asked to re consent and re-initiate treatment. This will occur at the next trial visit or at an unscheduled visit. These subjects will not receive the whole 48-week treatment. They will receive treatment for an additional 24 weeks minus the number of weeks that they have been in follow up.

Subjects that do not wish to re consent and re initiate treatment will stay in follow up and attend the follow-up visit as per the visit schedule outlined in Protocol Version 2.0 or 3.0.

At Baseline and at Weeks 4, 12, 24, 32 and 40 (Visits 2, 3, 5, 8, 10 and 12), dosing will take place in the clinic after blood sampling. A data review was conducted after the first 6 subjects had completed 12 weeks of treatment. If safety concerns or poor tolerability were identified in this review, the review committee might decide on less frequent dosing for subsequent subjects

in the study. The review was conducted on 16 September 2018 and concluded that there were no safety issues of significant concern and the dose was unchanged. In order to obtain more robust treatment responses it was decided to extend the treatment duration from 24 to 48 weeks. Any changes to the conduct of the study such as change of dose, dose regimen or duration will be documented in a protocol amendment.

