Subjects that do not wish to continue to 48 weeks of treatment will end treatment after 24 weeks (visit 8) and will attend the follow-up visit 12-weeks later as per the visit schedule outlined in Protocol Version 2.0 or 3.0.

Subjects who complete the initial 24-week treatment period prior to the approval of Protocol Version 4.0 will proceed to the 12-week follow up as per the visit schedule in Protocol Version 2.0 or 3.0. Once Protocol Version 4.0 is approved they will be asked to re consent and re-initiate treatment. This will occur at the next trial visit or at an unscheduled visit. These subjects will not receive the whole 48-week treatment. They will receive treatment for an additional 24 weeks minus the number of weeks that they have been in follow up.

Subjects that do not wish to re consent and re initiate treatment will stay in follow up and attend the follow-up visit as per the visit schedule outlined in Protocol Version 2.0 or 3.0.

At Baseline and at Weeks 4, 12, 24, 32 and 40 (Visits 2, 3, 5, 8, 10 and 12), dosing will take place in the clinic after blood sampling. A data review was conducted after the first 6 subjects had completed 12 weeks of treatment. If safety concerns or poor tolerability were identified in this review, the review committee might decide on less frequent dosing for subsequent subjects in the study. The review was conducted on 16 September 2018 and concluded that there were no safety issues of significant concern and the dose was unchanged. In order to obtain more robust treatment responses it was decided to extend the treatment duration from 24 to 48 weeks. Any changes to the conduct of the study such as change of dose, dose regimen or duration will be documented in a protocol amendment.

During the study, subjects in Group 1 will continue use of antimycobacterial treatment. All changes in antimycobacterial treatment will be recorded, including reasons for each change. In case of worsening of NTM pulmonary disease, antimycobacterial treatment may be added or a dosage increase of antimycobacterial treatment may be applied as rescue treatment, according to investigator's discretion.

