3.3.2 Study Terminology

Study-specific standard terms are detailed in Table 3.

Table 3: Study CDISC Terminology

Subject Elements	Screen (SCRN) Molgramostim (MOLG) Follow-Up (FU)
Epochs	SCREENING OPEN LABEL TREATMENT FOLLOW-UP
Treatment Arms	GROUP 1 GROUP 2
Visit Numbers / Visits	
SCREENING EPOCH
 
1.0 Screening
 
TREATMENT EPOCH
 
2.0 Baseline Visit*
 
3.0 Week 4
 
4.0 Week 8
 
5.0 Week 12
 
6.0 Week 16
 
7.0 Week 20
 
8.0 Week 24
 
9.0 Week 28
 
10.0 Week 32
 
11.0 Week 36
 
12.0 Week 40
 
13.0 Week 44
 
14.0 Week 48
 
888 Early Discontinuation
 
999 End of Study
 
FOLLOW-UP EPOCH
 
15.0 Follow Up Visit
 
Unscheduled visits: x.n where x is the visit number of the closest previous scheduled visit and n is the sequence number of the unscheduled visit, restarting at 1 after each scheduled visit. EPOCH will be assigned according to the epoch of the closest previous visit.
 
* “Baseline Visit” will be used when referring to Visit 2. The term “Baseline” will also be used as detailed in 3.3.3.

3.3.3 **Baseline**

For sputum data, baseline will be derived from the combined pre-treatment visits (i.e. Screening and Baseline), where at least one positive sample will be assigned as positive as baseline. For gradings, the most severe/highest grade will be used.

For all other parameters, baseline will be defined as the last available assessment prior to first study drug administration.

3.3.4 **Change from Baseline**

Absolute change from Baseline will be calculated as:

$$\text{Absolute change from baseline} = (\text{postbaseline value}) - \text{baseline value}$$

3.3.5 **Listings, Tables and Figures**

Listings, tables and figures will be delivered as individual .rtf files in accordance with the mock listings, tables and figures.

Data listings will present all data, with subjects grouped by Group.

Tabulations will summarise data by Group and Total.

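### SAP 8.1.1 counts the protocol-directed off-drug gap of re-starting subjects as exposure and as days on which a dose was due

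*SAP*

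**What the plan says.** Protocol 8.1 and SAP 2.1 set the same rule for subjects who reached Week 24 before Version 4.0 was in force. They enter the 12-week follow-up of the earlier protocol version. Then: "Once Protocol Version 4.0 is approved they will be asked to re consent and re-initiate treatment". For those who agree, "They will receive treatment for an additional 24 weeks minus the number of weeks that they have been in follow up". SAP 2.1 states the consequence itself: "These subjects will not receive the whole 48-week treatment".

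SAP 8.1.1 lists three derived variables in sequence:

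- a count, the "Number of subjects who had a break in treatment after completing Week 24 and commencing the remaining treatment period to Week 48";
- duration of exposure, which is the treatment discontinuation date minus the first treatment date, plus 1;
- overall compliance, which is used vials divided by treatment days, times 100, where treatment days run from Visit 2 to the end of treatment, plus 1.

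SAP 8.1.2 makes the last two reported outputs: "Duration of exposure and compliance (by visit and overall) will be summarised". SAP 5 names as one criterion for a critical deviation "Treatment compliance below 80 % during the treatment period". It does not say which compliance figure is meant.

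**The concern.** The SAP foresees the break and counts the subjects who had it, but the next two derivations ignore it. For a re-starter, the exposure variable is elapsed time and is not labelled as such. It would report a full 48 weeks for subjects who, by the SAP's own account, do not receive 48 weeks of drug.

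The compliance figure is harder to defend. No dose was due during the gap, yet each of those days sits in the denominator and lowers the percentage exactly as a missed dose would.

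What is at stake is the accuracy of the exposure and compliance tables in a 30-subject pilot, where exposure is the background for reading the safety data, and possibly the critical-deviation listing.

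**Working it through.** The documents state no exposure or compliance result to reproduce, so the check puts a fully adherent re-starter through the SAP formulas.

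**Inputs**

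- One dose daily (Protocol 8.1); one vial holds one 300 µg dose (Protocol 10.1 and 11.1).
- Visit 14 falls 336 days after Visit 2, with a window of ±7 days (Protocol Table 1).
- The last dose is taken the day before Visit 14 (Protocol 11.5), that is, on day 335 with Visit 2 as day 0.
- The first interval is 24 weeks, days 0 to 167, or 168 days.
- The gap is x weeks. The documents do not give it; 4, 8 and 12 weeks are assumed. Twelve weeks corresponds to a restart at the scheduled follow-up visit.
- The second interval starts on day 168 + 7x, lasts 168 − 7x days and ends on day 335.

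**Formulas**

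- Days on drug = 168 + (168 − 7x) = 336 − 7x, which is also the number of vials used.
- SAP exposure = 335 − 0 + 1 = 336 days for any x.
- SAP compliance = (336 − 7x)/336 = (48 − x)/48.
- Exposure overstatement = 7x days, or 7x/(336 − 7x) relative to days on drug.

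| Gap (assumed) | Days on drug | SAP exposure | Overstatement | SAP compliance |
|---|---|---|---|---|
| 4 weeks | 308 | 336 | 28 days (9.1%) | 308/336 = 91.7% |
| 8 weeks | 280 | 336 | 56 days (20.0%) | 280/336 = 83.3% |
| 12 weeks | 252 | 336 | 84 days (33.3%) | 252/336 = 75.0% |

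With the gap removed from both definitions, exposure equals days on drug and compliance is 100% in every row.

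**The 80% line.** (48 − x)/48 falls below 0.80 when x > 48 × 0.20 = 9.6 weeks. Shorter gaps do not cross the line on their own, but they use up the margin. Reaching 80% then needs true adherence of at least 0.80 × 336/308 = 87.3% with a 4-week gap, and 0.80 × 336/280 = 96.0% with an 8-week gap.

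**Other readings of the dates**

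- Visit 14 itself as end of treatment: 337 days; 91.4%, 83.1% and 74.8%.
- Visit 14 a week early or late: 329 or 343 days; 91.5–91.8%, 83.0–83.7% and 74.5–75.5%.
- The Week 24 stop as the end date, with all used vials counted: 168 days of exposure, and 308/168 = 183%, 280/168 = 167% and 252/168 = 150%.

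**Effect on the Total column (30 subjects, k re-starters assumed).** Mean compliance is understated by (k/30)(x/48), and mean exposure overstated by (k/30)(7x) days.

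| k | Gap | Compliance (points) | Exposure (days) |
|---|---|---|---|
| 1 | 8 weeks | 0.6 | 1.9 |
| 3 | 8 weeks | 1.7 | 5.6 |
| 6 | 4 weeks | 1.7 | 5.6 |
| 6 | 8 weeks | 3.3 | 11.2 |
| 6 | 12 weeks | 5.0 | 16.8 |

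The value k = 6 is an illustration. The safety review followed the first 6 subjects' completion of 12 weeks, and "The review was conducted on 16 September 2018". On schedule, those subjects would reach Week 24 no later than 84 days after that date, on 9 December 2018. Whether Version 4.0 had been approved by then is not stated.

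**The case against.** The strongest objection is that the SAP does not say which stop date applies to a subject who stops twice, so 336 days is one reading and not a stated result. That is true, but the other reading is worse: taking the Week 24 stop gives compliance of 150% or more over the assumed gaps. The final stop is also the natural reading, because the break variable refers to treatment continuing to Week 48. Neither choice gives a usable compliance figure.

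Several limits stand:

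- The 336-day figure needs an on-time Visit 14 and no early stop. The visit window moves compliance by about half a point, and a re-starter may discontinue early.
- The SAP 5 consequence is conditional. That section starts from recorded deviations, a directed gap is not a departure from the protocol, and its reference to the treatment period could be read as leaving the gap out. Visit-level compliance, a separate eCRF variable, might be the figure meant.
- The separate follow-up epoch in SAP Table 3 does not settle the matter. Only Visit 15 is placed there, and Weeks 28 to 48 are listed under treatment.
- The number of re-starters could be zero. The means above apply to the Total column only; the effect within Group 1 or Group 2 depends on group sizes and on how the re-starters divide, which the documents do not give.
- A reader could detect the interruption from the break count, the dispensing and administration listings, and the counts completing 24 and 48 weeks.

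A defence that elapsed time is an acceptable exposure measure would need the SAP to label it so. It would not help the compliance denominator, where days without a due dose count as missed.

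**Conclusion.** The concern holds. As written, SAP 8.1.1 reports directed time off drug as exposure and as non-compliance. For a fully adherent re-starter who finishes on schedule, exposure is overstated by 7x days and compliance understated by x/48. Over assumed gaps of 4 to 12 weeks, that is 28 to 84 days and 8.3 to 25.0 percentage points. The result rests on the final stop as end of treatment and on one vial per day on drug. The trial-level size cannot be fixed from the documents, because the number of re-starters, their gaps and the Version 4.0 approval date are not given.

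The damage is confined to the exposure and compliance summaries and, if SAP 5 uses the overall figure, to deviation reporting. There is a single analysis set, so nobody is excluded, and no efficacy result changes. The definitions should be corrected before the tables are produced.

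**What to change.** In SAP 8.1.1:

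1. Define duration of exposure as the sum of on-drug intervals. If elapsed duration is also wanted, report it alongside under that label.
2. Use on-drug days alone as the denominator of overall compliance.
3. State that end of treatment means the final stop.

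In SAP 5, state that the 80% criterion uses this gap-excluded figure.

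A smaller, separate improvement is to count the vials due at the dosing frequency recorded in the dose-change data, so that a recorded change of regimen is not read as non-compliance.

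The cost is SAP wording and derivation code. The SAP already requires subjects with a break to be identified, and it already collects clinic administration dates, kits dispensed by visit and dose-change start dates. One point to confirm when programming is that the first-interval stop date and the restart date can be recovered for each re-starter. The disposition listing in SAP 6 shows a single start and a single discontinuation date, and on-site dosing at an unscheduled restart visit is optional in the Protocol schedule.

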#### **8.4. Dose Adjustment Criteria**

A data review was conducted by a safety review committee comprised of the lead investigators and sponsor representatives after the first 6 subjects had completed 12 weeks of treatment. If safety concerns or poor tolerability were identified in this review, the review committee might decide on less frequent dosing for subsequent subjects in the study. The review concluded that no dose adjustment was required. Any changes to the conduct of the study such as change of dose regimen will be documented in a protocol amendment.

Subjects who experience poor tolerability to treatment (i.e. unacceptable respiratory or gastrointestinal symptoms, the nature of which may be assumed to be reversible) may reduce the dose. Prior to dose reduction, the Sponsor medical monitor must be consulted.

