## **11. STUDY DRUG MATERIALS AND MANAGEMENT**

### **11.1. Study Drug**

Each vial of molgramostim contains 300 µg molgramostim in 1.2 mL solution (250 µg/mL).

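### The SAP's compliance ratio cannot tell an agreed reduction in dosing frequency from missed doses, and the 80% critical-deviation criterion makes no exception for one

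*SAP*

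**What the plan says.** Protocol 8.1 sets the regimen: "Treatment with inhaled molgramostim will be given at a dosage of 300 µg once daily for 48 weeks". Protocol 11.1 gives the presentation: "Each vial of molgramostim contains 300 µg molgramostim in 1.2 mL solution (250 µg/mL"). One vial is therefore one nominal daily dose.

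Protocol 8.4 adds individual flexibility. Subjects with poor tolerability "may reduce the dose. Prior to dose reduction, the Sponsor medical monitor must be consulted". It does not say whether such a reduction is in frequency or in amount. The option it describes for the safety review committee was less frequent administration.

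SAP 8.1.1 derives overall compliance as the number of used vials divided by treatment days, times 100. Treatment days are all calendar days from Visit 2 to the end of treatment, inclusive. The same section collects, for each dose change, the start of the new regimen, the number of doses, the frequency and the reason. SAP 8.1.2 lists those details, and then: "Duration of exposure and compliance (by visit and overall) will be summarised".

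SAP 5 classes recorded deviations as minor or major and assesses the major ones further for critical status. One of its two criteria for critical status is "Treatment compliance below 80 % during the treatment period". It states no exception for a reduction agreed under Protocol 8.4, and it does not say which compliance figure it uses.

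**The concern.** A compliance percentage is normally read as adherence: what share of the doses they were told to take did subjects take? The SAP ratio answers that question only while the agreed regimen is one vial a day. Once a subject is moved to fewer dosing days, the numerator falls and the denominator does not. Following the agreed plan and skipping doses then produce the same number.

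The 80% criterion inherits the ambiguity. A subject whom the protocol allows to reduce could be counted beside subjects who did not take their treatment.

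This is a pilot meant to inform a later phase II programme (Protocol 6.3). How many subjects tolerated daily dosing and how many failed to adhere are separate findings for that purpose. With 30 subjects, each one classified wrongly moves an overall percentage by 1/30 = 3.3 points, and by more within a group.

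The other planned summaries do not separate the two either. Duration of exposure is a count of calendar days, the disposition table in SAP 6 has no row for dose reduction, and the actions taken with study drug in SAP 10.2.1 do not include one. Reductions appear only in listings.

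**Working it through.** The documents report no compliance figure to reproduce, so the check applies the SAP formula to subjects who adhere perfectly to a reduced frequency.

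**Inputs from the documents**
- Planned treatment: 48 weeks × 7 = 336 days (Protocol 8.1).
- One 300 µg vial per nominal daily dose (Protocol 8.1, 11.1).
- Compliance = used vials / treatment days × 100 (SAP 8.1.1).
- Critical-deviation criterion: below 80% (SAP 5).

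**Assumption, for illustration only.** The reduced frequencies below are not in the documents and are not proposed. They show how the formula behaves.

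**Reference case.** Daily dosing throughout gives 336/336 = 100%.

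**Alternate-day dosing from a given week, every agreed dose taken.** With d days of daily dosing first, used vials = d + (336 − d)/2.

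| Switch at | Used vials | Compliance | Below 80%? |
|---|---|---|---|
| Week 4 | 28 + 154 = 182 | 54.2% | yes |
| Week 12 | 84 + 126 = 210 | 62.5% | yes |
| Week 24 | 168 + 84 = 252 | 75.0% | yes |
| Week 28 | 196 + 70 = 266 | 79.2% | yes |
| Week 32 | 224 + 56 = 280 | 83.3% | no |
| Week 40 | 280 + 28 = 308 | 91.7% | no |

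**Crossover.** With f the fraction of treatment completed before the switch, compliance is f + (1 − f)/2. Setting this to 0.80 gives f = 0.60, which is 0.60 × 336 = 201.6 days, or Week 28.8.

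**Other frequencies from day 1, every agreed dose taken**
- 2 days in 3: 224/336 = 66.7%.
- 5 days in 7: 240/336 = 71.4%.
- 6 days in 7: 288/336 = 85.7%, which is not below 80% but is still short of 100% for a fully adherent subject.

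**Same subject, prescribed-dose denominator.** Alternate-day dosing from day 1 scores 168/336 = 50% under the SAP formula and 168/168 = 100% against the doses prescribed.

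**What the SAP ratio does measure.** For a frequency reduction, 182 vials × 300 µg = 54.6 mg out of 336 × 300 µg = 100.8 mg, which is 54.2%. This equals the compliance score in the first row of the table. The ratio is correct as the delivered fraction of the nominal regimen; it is not a measure of adherence.

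**The case against.** The strongest reply is that the ratio is not wrong. With one vial per dose it gives exactly the share of once-daily dosing that was delivered. That stands, and it is why the ratio should be kept under a different label. A reader might infer that every exposure summary misstates what reduced subjects received. It does not: for a frequency reduction the delivered fraction is right, and duration of exposure is merely insensitive to the change.

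A reader might also infer that every reduced subject becomes a critical deviation, or else looks fully dosed. The figures rule this out: 6 days in 7 scores 85.7%, and alternate-day dosing from Week 32 scores 83.3%.

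Nor is critical status shown to be automatic. SAP 5 starts from recorded deviations, and a reduction made under Protocol 8.4 follows the protocol and may never be recorded as one. SAP 5 also does not name the overall figure, and SAP 8.1.1 holds a visit-level compliance variable as well. These are fair limits on the claim. But SAP 8.1.1 contains the only compliance formula in the SAP, so the unstated link is itself something to settle.

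A further inference would be that a subject inhaling part of a vial each day would score 100% and so conceal a reduction. No passage describes part-vial use: the unit dose is 300 µg (Protocol 10.1), drug preparation is given as not applicable (Protocol 11.4), and the SAP's dose-change fields cover number and frequency of doses. The point does not rely on it.

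Finally, SAP 4 defines only the FAS, so a critical deviation excludes nobody and no conversion rate or interval changes. That also stands, and it confines the point to compliance and deviation reporting.

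**Conclusion.** The point holds for reductions in dosing frequency. SAP 8.1.1, SAP 5 and Protocol 8.4 do not fit together: the formula treats one vial per calendar day as the standard for everyone, the protocol permits individual departures from that standard, and the 80% criterion cannot separate those departures from missed doses.

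A subject who takes every agreed dose can score well below 100%, and below 80% if the reduction is large or early. On the alternate-day illustration the score is 54.2% to 75.0% for a switch between Weeks 4 and 24, with the threshold crossed at Week 28.8.

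This rests on two assumptions: that a reduction takes the form of fewer dosing days, which Protocol 8.4 leaves open, and that the 80% criterion is applied to the overall ratio, which SAP 5 does not state. The documents do not say how many subjects reduced their dose, so the number affected is unknown. The consequence is limited to reported compliance and the critical-deviation count.

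**What to change.** In SAP 8.1.1, define compliance as doses taken divided by doses prescribed under the regimen in force, times 100. Build the denominator from the dose-change fields already collected: start date, number of doses and frequency. In SAP 5, state that the 80% criterion uses this figure.

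Keep the present ratio, relabelled as the delivered fraction of the nominal once-daily regimen. Add a table of subjects with any dose reduction, by group and in total, so that reductions appear in a summary as well as in listings.

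The cost is SAP wording, one more derived variable, a short table and a small programming change; no new data field is needed. The two percentages will need clear labels so that they are not confused. No dose or reduction rule is proposed. What is asked is that Protocol 8.4, SAP 5 and SAP 8.1.1 be reconciled.
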